8.2 Overall Study Design

Subjects who complete treatment and assessments in the other BAX 855 studies and BAX 855-naïve subjects who fulfill the inclusion/exclusion criteria will be eligible to participate in this continuation study. Approximately 250 PTPs with severe hemophilia A will be enrolled to achieve 200 evaluable subjects. This study was designed to be in compliance with EMA/CHMP/BPWP/144533/2009⁶ recommendations for the study of FVIII in severe hemophilia A.

The subject's hemophilia history, bleeding episode history, and FVIII usage and treatment regimen(s) within the previous year will be collected at screening for BAX 855 naïve subjects. Results of the screening assessments will be used to establish subject's eligibility for this study and may serve as baseline measurements. Subjects transitioning from the other BAX 855 studies may use end of study assessments in their prior study for screening assessments in this continuation study.

Once eligibility is established, subjects can choose to receive either a fixed BAX 855 prophylaxis or a PK-tailored BAX 855 prophylaxis (as described in Section 8.7.3). Subjects will also treat breakthrough bleeding episodes with BAX 855. Details on bleeding episodes, the number of infusions used for treatment, and the efficacy of treatment (based on a 4-point rating scale; see Section 11.2) will be recorded in an electronic diary (e-diary). Subjects will be treated with BAX 855 for a minimum of 100 EDs (accumulated across all BAX 855 studies they have participated in).

Transitioning subjects receiving a fixed dose prophylactic treatment regimen will return to the study site at 6 weeks following screening to confirm eligibility and at this visit and subsequent visits every 3 months following screening, IR will be determined, efficacy and safety will be assessed and e-diary will be reviewed. BAX855 naïve subjects with

confirmed eligibility will undergo their baseline visit for determination of IR at exposure day 1 (ED1) and return to the study site after 6 weeks and every 3 months following their baseline visit for IR determination, efficacy and safety assessment and e-diary review.

Subjects receiving a PK-tailored prophylactic treatment regimen will have their PK assessment performed following eligibility confirmation. Following PK assessment, they undergo their baseline visit and subsequent visits every 3 months following their baseline visit for IR determination, efficacy and safety assessment and e-diary review. In addition, at 4, 8 and 18 weeks after the baseline visit, subjects' FVIII levels, TGA parameters and VWF antigen will be measured to ensure that FVIII trough levels of $\geq 3\%$ are maintained, and, if necessary, dose adjustments will have to be performed. Also, hemostatic efficacy and clinical safety will be assessed and e-diary reviewed.

Investigators will review e-diaries for untoward events, concomitant medications, non-drug therapies, and patient reported outcomes (PROs; see Section 10.5.2). Safety assessments performed at the study visit will include immunogenicity (inhibitory antibodies for FVIII and binding antibodies for FVIII, BAX 855, PEG, and CHO), and changes in conditions of the physical examination, vital signs, and clinical laboratory assessments (hematology, clinical chemistry, and lipids). Subjects who develop a high responder inhibitor (> 5 Bethesda Units [BU]), or who develop a low responder inhibitor (≤ 5 BU but ≥ 0.6 BU) that cannot be adequately managed by the prescribed prophylaxis regimen with BAX 855 will be discontinued from study. At every study visitⁱⁱⁱ, IR for FVIII activity and TGA parameters (optional in subjects receiving fixed dose prophylaxis) will be determined within 30 minutes prior to infusion with 60 ± 5 IU/kg BAX 855 and 30 ± 15 minutes following the infusion. Also, TGA parameters and pre-infusion VWF antigen level will be assessed in subjects receiving a PK-tailored dosing (optional for subjects aged < 12 years).

The sponsor will suspend enrollment and treatment if 2 or more subjects develop anaphylaxis after BAX 855 treatment. The sponsor may stop this study at any time. In addition, the sponsor may modify the study based on results of the other BAX 855 studies.

8.3 Duration of Study Period(s) and Subject Participation

The overall duration of this continuation study is estimated to be approximately 4 years from study initiation (ie, first subject enrolled by signing informed consent) to study

ⁱⁱⁱ Except at visits 4 ± 1 , 8 ± 1 and 18 ± 2 weeks following baseline in those subjects receiving PK-tailored treatment regimen.

completion (ie, last subject last visit). Recruitment of transitioning subjects will continue until the last subject has completed any other BAX 855 study.

Each subject will participate in the study until a total of at least 100 EDs to BAX 855 has been achieved (accumulated across all BAX 855 studies in which each subject participated). Depending on the subject's BAX 855 exposure history and treatment regimen given, the planned duration of subject participation to reach the 100 EDs (from enrollment to subject completion) can vary from approximately 3 to 12 months. However, extension of the study duration for individual subjects beyond the 100 EDs may be granted.

8.4 Outcome Measures

8.4.1 Primary Outcome Measures

8.4.1.1 Safety

- Development of inhibitory antibodies to FVIII

8.4.1.2 Efficacy

- Spontaneous ABR

8.4.2 Secondary Outcome Measures

8.4.2.1 Efficacy

1. Total ABR (spontaneous and traumatic bleeding episodes)
2. Overall hemostatic efficacy rating of BAX 855 for treatment of breakthrough bleeding episodes
3. Number of BAX 855 infusions to treat bleeding episodes
4. Time intervals between bleeding episodes
5. Weight-adjusted consumption of BAX 855

8.4.2.2 Safety

1. Occurrence of AEs and SAEs
2. Changes in vital signs and clinical laboratory parameters (hematology, clinical chemistry, and lipids)
3. Immunogenicity
 - a. Binding antibodies (IgG and IgM) to FVIII, BAX 855, and PEG
 - b. Anti-CHO antibodies

8.4.2.3 Patient Reported Outcomes

Changes from baseline in parent study, if applicable, in the following:

1. Bleed and pain severity as measured using the Haemo-SYM questionnaire
2. HRQoL as assessed using the SF-36/PedsQL questionnaires

8.4.3 Exploratory Outcomes Measure

1. Patient satisfaction with treatment will be assessed using the Satisfaction Question Set
2. Patient Activity Level
3. Health resource use data (eg, physician office visits, hospitalizations, days missed from work/school)
4. TGA parameters, FVIII trough levels and ABR

8.5 Randomization and Blinding

This is a non-randomized, open-label, active treatment clinical study.

8.6 Study Stopping Rules

This study will be stopped if 1 or more of the following criteria are met:

Enrollment and treatment in this continuation study will be suspended or stopped, if the following criterion is met:

1. If 2 or more subjects develop anaphylaxis following exposure to BAX 855

The study may be terminated, if one or more of the following criteria are met:

1. The sponsor decides to terminate the study based upon its own assessment of safety
2. The sponsor decides to terminate the study for administrative reasons

8.7 Investigational Product(s)

8.7.1 Packaging, Labeling, and Storage

BAX 855 is formulated as a sterile, highly purified protein preparation in lyophilized form for i.v. infusion and is provided in single-dose vials along with a vial of diluent (2 or 5 mL SWFI, as available). A butterfly transfer set with luer-lock syringes and a needleless transfer device will be used for reconstitution and bolus i.v. delivery (BAXJECT II high-flow [HF] and BAXJECT III, as available). The BAXJECT system is a needleless liquid transfer device with the primary function of transferring diluent from

its vial into an evacuated vial containing product requiring reconstitution prior to infusion.

A minimum of 4 lots of BAX 855 manufactured for this study will be used. Four nominal potencies of BAX 855 will be used, depending upon availability: 250, 500, 1,000 and 2,000 IU/vial.

The recommended storage conditions for BAX 855 are 2°C to 8°C (36°F to 46°F) and it should not be allowed to freeze. BAX 855 should be stored and protected from light. The reconstituted product should ideally be used immediately but no longer than 3 hours after reconstitution.

For additional information, such as reconstitution instructions, refer to the BAX 855 IB and/or other specific instructions provided by the sponsor.

8.7.2 Administration

Following reconstitution, BAX 855 should be administered using plastic syringes provided by the sponsor since proteins such as BAX 855 may adhere to the surface of glass syringes. BAX 855 will be administered i.v., using an appropriately sized syringe, as a bolus infusion over a period of ≤ 5 minutes with a maximum infusion rate of 10 mL/min, as described in the BAX 855 IB. The reconstituted BAX 855 must be administered at room temperature and within 3 hours.

BAX 855 dose calculation will be based on the stated actual potency on vials in respective lots.

PK assessment and determination of IR

For the PK assessment in individual subjects, only vials of the same lot with a nominal potency of 500 IU should preferably be used. Alternatively, 1000 IU vials of the same lot could be used.

- In subjects aged ≥ 12 years: total calculated dose may be rounded up to the nearest whole vial in case 500 IU potency vials are used. However, in case vials with a nominal potency of 1,000 IU/vial are used, the total calculated dose should not be rounded up to the nearest whole vial to ensure accurate dosing (eg, 2.5 vials).
- In subjects aged < 12 years: The exact amount of IUs has to be administered irrespective of the potency used (eg, 1.5 vials).

Infusions for prophylaxis and treatment of bleeding episodes

Two different lots per infusion may be used, however, each vial must be reconstituted with its own kit. The total calculated dose can be rounded up to the nearest whole vial.

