6.3 Population To Be Studied

Approximately 250 PTPs with severe hemophilia A, of any ethnic group, aged ≤ 75 years, will be enrolled to achieve a total of 200 evaluable subjects. Each subject will have ≥ 100 EDs with BAX 855, as accumulated across all BAX 855 studies in which the subject participates.

Justification for enrollment of pediatric subjects is based on the nonclinical safety requirements outlined in the ICH M3 Guideline, Section 12 as well as the ICH E11 Guideline on clinical investigation of medicinal products in the pediatric population. Hemophilia is a serious and potentially life-threatening disease. Pediatric subjects are expected to benefit from a full-length rFVIII molecule with an extended half-life. Moreover, results from nonclinical repeated toxicology studies, the core safety pharmacology package, and the clinical phase 1 study have not raised any safety or tolerability concerns. Furthermore, the parent protein molecule ADVATE has been used extensively in the entire pediatric population with no unforeseen adverse events (AEs) (refer to the ADVATE IB). BAX 855 naïve subjects < 12 years of age will not be enrolled in this continuation study until enrollment in the BAX 855 pediatric PTP study in children aged < 12 years (Study 261202) has been completed. In accordance with the EMA/CHMP/BPWP/144533/2009 guideline⁶, the study in pediatric PTPs < 12 years of age (Study 261202) will only be initiated once PK, hemostatic efficacy and safety data of 20 PTPs aged ≥ 12 years treated with BAX855 for at least 50 EDs are available and evaluated by an independent DMC for its safety and efficacy. At least 60 evaluable subjects in this BAX 855 continuation study must be < 12 years of age.

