8.7.3.1 Fixed Dose Prophylactic Treatment Regimen

The fixed dose prophylactic treatment regimen with BAX 855 will be age-dependent as follows:

- Subjects aged ≥ 12 years: 45 ± 5 IU/kg twice weekly, which may be increased up to 80 IU/kg
- Subjects aged < 12 years: 50 ± 10 IU/kg twice weekly, which may be increased up to 80 IU/kg

Subjects must adhere as closely as possible to the dosing regimen. The days of the week on which treatment is administered may be selected by the subject and/or his/her physician and should be selected to provide maximum coverage for vigorous activities. Dosing must be administered twice weekly, at 3 and 4 day intervals (Option X), or 3.5 day intervals (Option Y with AM and PM dosing) and should be maintained during the study (Table 2). If a dose is missed, it must be documented and the next dose will be taken as soon as possible. After this dose, the regularly scheduled regimen will be resumed. For example, in Option X, if twice weekly dosing is scheduled for every Monday and Thursday and the subject misses the Thursday dose, he/she should infuse the next dose on Friday and then resume his/her schedule with subsequent dose on Monday). And for Option Y, if dosing is scheduled for the morning on Monday and the evening dose on Thursday, and the subject misses the Thursday dose, he/she should infuse the

iv Please note that subjects who are on a 30-80 IU/kg every 5 days (q5d) or every 7 days (q7d) treatment regimen prior to this protocol amendment 4 (dated 23 May 2014) being effective can decide to continue on their 30-80 IU/kg q5d or q7d treatment regimen after this protocol amendment 4 (dated 23 May 2014) is effective. These subjects will then follow the procedures as described for transitioning subjects on a fixed dose prophylactic treatment regimen (see also Supplement 20.3.1). Additionally, these subjects can decide to switch to a fixed dose or PK-tailored prophylactic treatment regimen as per protocol amendment 4 (dated 23 May 2014) at any time during the study.

next dose on Friday morning, and then resume his/her schedule with a subsequent dose on Monday morning.

Table 2 BAX 855 Example Dosing Frequency							
Day	Mon	Tue	Wed	Thu	Fri	Sat	Sun
Morning	X or Y			X			
Evening				Y			

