#### 4.4 Per Protocol Analysis Set (PPAS)

The per protocol (PPAS) analysis set is to comprise all subjects in the FAS who had no major deviations from the protocol affecting the study results. Protocol deviations are to be obtained from the Clinical Trial Management System (CTMS).

Prior to performing any analysis as set out in this SAP, a meeting is to be held discussing the impact of any major protocol deviation on the analysis. At this meeting, the decision is to be made on whether a subject is to be excluded from the PPAS analysis set or not. The meeting is to be attended by participants from at least Biostatistics and Medical.

Below is a list of possible major deviations that may influence the study results that will be discussed at the analysis set assignment meeting:

- Subject less than 75% exposed to BAX 855 as derived in Section 6.8: Measurements of Treatment Compliance.
- Subject less than 75% compliant to planned dosing regimen.
- More than 10% of treated bleeds have no efficacy rating.
- Use of expired IP.
- Subject did not reach 100 EDs across all BAX 855 studies.
- Use of any FVIII product other than ADVATE, as determined by the medical team.

It should be noted that the above will not necessarily lead to immediate exclusion from the PPAS, but will be discussed prior to locking the database. The database is not allowed to be locked until final approval on the PPAS has been obtained.

During the course of the study, data review meetings are to be held on a regular basis. During these meetings the quality of the data including any potential protocol deviations are to be identified. All protocol deviations identified at these meetings are to be included into the CTMS upon team agreement.

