## 6.7 Extent of Exposure

The following information is to be obtained from the eCRF:

- Information on study infusions (*Study Infusions* eCRF panels).
- Treatment regimen, including planned dose (*Treatment Assignment* and *Change of Treatment Assignment* eCRF panels).
- Body weight (*Vital Signs* eCRF panels).

The following derivations based on eCRF reported results are to be performed:

- Body weight-adjusted dose (IU/kg) is to be derived as the total units infused (IU) divided by the last available body weight (kg) prior to the infusion. Refer to Section 5.4: Handling of Missing, Unused, and Spurious Data for imputation schemes to be implemented.
- Total number of infusions in this study are determined as the count of the number of infusions, regardless of date and time, the subject had. Number of infusions are to be determined overall and by reason for infusion as well as by the treatment regimen assigned to at the time of receiving the treatment.
- The number of EDs are determined as the number of unique calendar days on which a subject received any or part of any infusion. Multiple infusions on the same day are still to be considered one ED. EDs are to be determined overall as well as for each reason an infusion is given. The number of EDs will be determined for this study and across all previous BAX 855 studies the subject participated in. EDs in this study will be derived as the number of infusions on unique calendar days in this study, while EDs from previous BAX 855 studies will be obtained as reported in the eCRF. The total EDs across all BAX 855 studies will be determined as the sum of EDs in current study and EDs in previous studies.
- The observation period for efficacy (OPE) in days in the study for subjects who never transferred to the surgery study is to be determined as:

$$OPE(Days) = (Stop\ Date - Start\ Date) + 1$$
 where "Start Date" refer to the first BAX 855 infusion in the current study and "Stop Date" to the last BAX 855 infusion in the current study. For subjects on the PK-guided regimen, first BAX 855 infusion will be the first prophylactic infusion.

• The OPE in days for subjects that did transfer to the surgery study is to be determined as:

$$OPE(Days)$$

$$= (Date\ of\ Transfer\ to\ Surgery\ Study - Start\ Date) + (Stop\ Date - Return\ Date\ to\ Current\ Study) + 1$$
where "Start\ Date" and "Stop\ Date" are\ defined\ as\ above.

• The OPE in weeks is to be determined from the OPE in days as:

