#### **6.8** Measurements of Treatment Compliance

Treatment compliance is to be derived using results and derivations obtained from study exposure as described in Section 6.7: Extent of Exposure.

Treatment compliance is to be based on the following:

- Adherence to the infusion schedule; and
- Adherence to recommended prophylactic dose.

An infusion is considered to be in adherence to the infusion schedule if:

- Time since last infusion on the "twice weekly regimen" do not exceed 5 days.
- Time since last infusion on the "every 5 day regimen" do not exceed 5 days.
- Time since last infusion on the "every 7 day regimen" do not exceed 7 days.
- Time since last infusions on the "other dosing regimen" do not exceed the days specified by the investigator.

Based on the treatment regimen, time that a subject was not exposed to BAX 855 is to be determined. Time a subject was not exposed to BAX 855 is to be derived as:

- = Days since last BAX 855 infusion
- Treatment regimen allowed days

Time not exposed (days) is to be set to 0 days if the above derivation results in number of days less than 0. The total time not exposed to BAX 855 for each subject will be determined as the sum of times not exposed for each individual infusion.

The percentage of time a subject was exposed to BAX 855 is to be derived as follows:

$$\textit{Time Exposed (\%)} = \frac{\textit{OPE(Days)} - \textit{Total Time not Exposed (Days)}}{\textit{OPE(Days)}} \times 100$$

An infusion is considered to be in adherence to the recommended prophylactic dose if the actual amount infused (IU/kg) are between 90% and 110% of the planned dose (IU/kg) to be infused. Infusions with actual amount infused not recorded in the eCRF are to be excluded from the compliance calculations.

The number and percentage of infusions in adherence to the recommended prophylactic dose will be determined for each subject and treatment regimen using the overall number of infusions for that subject as denominator.

Treatment compliance are to be summarized for the SAS and PPAS and listed for the SAS. Summaries are to be presented by age category and treatment regimen at time of dose on a subject level.

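### SAP 6.8 scores infusions above 110% of the planned dose as non-adherent with no allowance for permitted whole-vial rounding, so correctly dosed light children can be misclassified if the planned dose is the pre-rounding target

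*Protocol*

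**What the plan says.** Protocol 8.7.2, on infusions for prophylaxis and bleeding episodes: "The total calculated dose can be rounded up to the nearest whole vial". No age limit is attached. The requirement to give under-12s the exact number of units stands under the separate heading for PK and incremental-recovery infusions.

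Protocol 8.7.3.1 sets the fixed regimen for children: "Subjects aged < 12 years: 50 ± 10 IU/kg twice weekly, which may be increased up to 80 IU/kg". From 12 years it is 45 ± 5 IU/kg. On vials, protocol 8.7.1 says: "Four nominal potencies of BAX 855 will be used, depending upon availability: 250, 500, 1,000 and 2,000 IU/vial".

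SAP 6.8 counts an infusion as adherent to the recommended dose "if the actual amount infused (IU/kg) are between 90% and 110% of the planned dose (IU/kg) to be infused". The only infusions it leaves out are those with no recorded amount. It then says: "Summaries are to be presented by age category and treatment regimen at time of dose on a subject level".

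SAP 6.7 takes "Treatment regimen, including planned dose" from the Treatment Assignment forms. Neither document says whether that entry is made before or after vial rounding.

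SAP 4.4 lists among possible major deviations: "Subject less than 75% compliant to planned dosing regimen". It adds that listed items are discussed before database lock and do not necessarily lead to exclusion.

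**The concern.** The protocol and the SAP use different tolerances for a correct prophylactic dose. Around a planned 50 IU/kg the SAP accepts 45 to 55 IU/kg, while the protocol's window is 40 to 60 and rounding is only upward. A child given a dose above 55 and up to 60 IU/kg has been treated as the protocol allows, yet fails the SAP's test. The same weight and vials give the same excess at every infusion, so the error does not average out within a child: dose adherence can sit near 0% until weight or vial size changes.

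Two outputs are exposed. The first is the compliance summary by age category, where the artefact would look like poorer adherence in the youngest subjects. This matters because protocol 6.3 states: "At least 60 evaluable subjects in this BAX 855 continuation study must be < 12 years of age". The second is the per-protocol set, if the 75% criterion in SAP 4.4 means the dose measure of SAP 6.8. SAP 7.1 reports the bleeding-rate models on that set as well as on the full analysis set.

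**Working it through.** The plan gives no figure of its own here; 90% to 110% is a rule. The check asks how often permitted rounding breaks it.

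**Inputs from the documents.** Band 90% to 110% (SAP 6.8); windows 40 to 60 IU/kg under 12 and 40 to 50 IU/kg from 12 (protocol 8.7.3.1); vials of 250 and 500 IU (protocol 8.7.1); rounding up allowed (protocol 8.7.2).

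**Assumptions, not in the documents.** Planned dose is the pre-rounding target: 50 IU/kg under 12, 45 IU/kg from 12. Weights are uniform over 10 to 40 kg and 40 to 100 kg. One vial size at nominal potency. Rounding always used.

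**Formula.** For weight W, planned dose t and vial size v, infused dose = ceil(tW/v) × v / W, compared with 1.1t (55 IU/kg for t = 50; 49.5 IU/kg for t = 45).

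**Single cases, planned 50 IU/kg**
- 13 kg, 250 IU vials: 650 IU becomes 750 IU; 750/13 = 57.7 IU/kg; 57.7/50 = 115%.
- 17 kg, 500 IU vials: 850 IU becomes 1,000 IU; 58.8 IU/kg; 118%.
- 26 kg, 500 IU vials: 1,300 IU becomes 1,500 IU; 57.7 IU/kg; 115%.

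All three lie within 40 to 60 IU/kg.

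**Share of weights above 110% but at or below 60 IU/kg.** With n vials this needs max((n−1)v/50, nv/60) < W < nv/55.
- v = 250: 12.5–13.6, 16.7–18.2, 20.8–22.7, 25.0–27.3, 30.0–31.8 and 35.0–36.4 kg. Total 10.0 of 30 kg = 33.3%.
- v = 500: 16.7–18.2, 25.0–27.3 and 33.3–36.4 kg. Total 6.8 of 30 kg = 22.7%.

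**The cap matters.** Protocol 8.7.2 does not say that rounding must stop at the window's upper limit. Dropping the nv/60 condition, and repeating for 45 IU/kg over 40 to 100 kg:

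| | 250 IU vials | 500 IU vials |
|---|---|---|
| Under 12, above 110% and at most 60 IU/kg | 33.3% | 22.7% |
| Under 12, above 110%, no cap | 15.0/30 = 50% | 21.8/30 = 73% |
| 12 or over, above 110% and at most 50 IU/kg | 2.3% | 6.6% |
| 12 or over, above 110%, no cap | 1.9/60 = 3% | 20.6/60 = 34% |

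With 500 IU vials the ratio of children to older subjects is 22.7/6.6 = 3.4 with the cap and 73/34 = 2.1 without it. The direction holds; its size depends on the vial and on the cap.

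**Sensitivity to the planned dose** (under 12, with the 60 IU/kg cap, 250/500 IU vials): 49.9%/52.0% at 45 IU/kg, 33.3%/22.7% at 50, 5.9%/2.5% at 54, and 0% at 55, where 110% is already 60.5 IU/kg.

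**The case against.** The strongest objection is that SAP 6.8 compares each infusion with the subject's own planned dose, not with 50 IU/kg. If sites enter the already rounded IU/kg as planned, nothing is misclassified. This stands as a condition on the whole point. The documents do not settle it, which is itself a reason to state the convention.

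Second, adherence to the prescribed dose and presence in a protocol window are different measures, and a sponsor may choose the first. That also stands. But a dose rounded up as the protocol allows is not a departure from the prescription, so the first measure still needs a rounding allowance.

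Third, SAP 4.4 speaks of the planned dosing regimen, and SAP 6.8 uses regimen as a label for infusion schedules. Under a schedule reading, rounding never triggers the criterion. SAP 4.4 does list exposure time as a separate item, which favours the dose reading, but the text does not decide it.

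A reader might infer more than the documents support:
- That children will be dropped from the per-protocol set. Flagged subjects are only discussed, at a meeting attended by at least Biostatistics and Medical.
- That spontaneous bleeding rate, the co-primary efficacy outcome, is biased. Protocol 13.2.2 places efficacy analyses on the full analysis set, which this rule does not touch.
- That the percentages convert to a count among the 60 children. That would need every child to be on fixed dosing, planned at 50 IU/kg and always rounded. Subjects may choose PK-tailored dosing, where the 40 to 60 window does not apply, and rounding is optional.

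**Conclusion.** The point holds conditionally. If the recorded planned dose is the pre-rounding target, SAP 6.8 misclassifies doses that the protocol permits, and light children bear most of it. Under the stated assumptions, 33% (250 IU vials) or 23% (500 IU) of weights under 12 give a dose above 110% yet within the window; 50% or 73% exceed 110% if rounding is not capped, against 3% or 34% from 12 years. These are shares of assumed weights, not forecasts of affected subjects. They fall with less frequent rounding, mixed vial sizes or a planned dose nearer 55 IU/kg.

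The certain consequence, given that condition, is a distorted compliance summary by age. Needless referral to the per-protocol discussion is possible, depending on what SAP 4.4 means. The primary analyses are unaffected. The change is worth making because it is small and the error is systematic.

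**What to change.** In SAP 6.8:
- Keep the 90% lower limit, relative to the subject's current planned dose.
- Count an infusion above 110% as adherent if the excess is explained by rounding planned IU/kg × weight up to the nearest whole vial.
- For subjects not escalated above the standard regimen, also count it as adherent if the dose is within the upper limit of protocol 8.7.3.1 (60 IU/kg under 12, 50 IU/kg from 12).
- State that the planned dose is the target before rounding.

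In SAP 4.4, name the SAP 6.8 measure that the 75% criterion uses.

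Do not accept every dose in the 40 to 60 (or 40 to 50) IU/kg window. Fixed dosing may be raised to 80 IU/kg, and a child escalated to 80 who infuses 40 (40/80 = 50% of plan) must stay flagged. The 90% floor does that.

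The cost is a slightly more complex derivation and a few clarifying sentences. Units infused, weight and planned dose are already drawn from the eCRF. The rounding test also needs the vial potency, which SAP 6.7 does not list by name, so confirm that it is captured. The downside is that overdosing caused by rounding is no longer flagged. This is usually mild, but at 10.1 kg with 500 IU vials, 505 IU becomes 1,000 IU, or 99 IU/kg. I would therefore end the rounding allowance at the 80 IU/kg maximum in protocol 8.7.3.1.
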